### [12.5. Analytical Approach for Cohort Analyses](#)

The analyses for each cohort uses the same analysis for the primary models (ordinal, dichotomous, and time-to-event) with the following differences. For each model the treatment effect is modeled separately and independently in each defined cohort. A single group will be selected as the group to have a main effect treatment effect, modeled with a normal distribution with mean 0 and standard deviation 10 (for the log-odds or log-hazard ratio). This group is either the largest group or the first subgroup. Each additional group will have an additive effect on the log parametrization scale with independent normal distribution priors with mean 0 and standard deviation 10.

If multiple subtypes are reported in a single analysis, each group within each subtype will be modeled independently without Bayesian borrowing across subtypes for the treatment effect.

### [12.6. Markov Chain Monte Carlo \(MCMC\) Model Stability](#)

The Bayesian models have many parameters and there may be risk of poor model stability, including convergence and mixing behavior of the MCMC sampler. These instabilities may be based on sparse data on the outcome or covariates. The statisticians running the model may make changes that do not affect the overall interpretation but provide reliable model diagnostics and scientific rigor. Any alterations will be noted.

### [12.7. Model Outputs](#)

The standard model outputs for each treatment effect will be the mean, standard deviation, median, and 95% credible intervals (all credible intervals will be equal-tailed intervals, so 95% credible intervals will range from the 2.5th percentile to the 97.5th percentile of the posterior distribution). For the ordinal endpoints, the odds ratios will be summarized. For the dichotomous endpoints, the odds ratios will be summarized. For the time-to-event endpoints, the hazard ratios will be summarized. **For consistency, all models will be parameterized so that an odds ratio or hazard ratio greater than 1 indicates clinical benefit.**

For each inferential model, a posterior probability that one arm is superior will be provided for each comparison between arms. This posterior probability has been identified as the primary analysis metric between arms. A posterior probability greater than 99% of superiority or inferiority has been identified as statistically significant. For futility a threshold of 95% has been specified.

### [12.8. Exploratory Analyses](#)

Exploratory analyses after unblinding will not be considered inferential and no p-values will be presented. Any post-hoc exploratory analyses will use the following methods:

1. Ordinal endpoints will be compared using a cumulative proportional odds model with summaries of the OR, 95% confidence intervals, and Wilcoxon tests for robustness against a lack of proportional odds.
2. Time-to-Event analyses will utilize a Cox proportional hazards model, summarizing the hazard ratios and 95% confidence intervals.
3. Continuous endpoints will compare means with 95% confidence intervals based on two-sample t-test procedures.
4. Dichotomous proportions will be compared using logistic regression summarizing the OR and 95% confidence intervals. Differences between proportions will be summarized using observed differences and normal approximations for the 95% credible intervals.

#### [12.9. Handling of missing data](#)

For the primary endpoint of OSFDs missing primary outcomes will be ignored. A sensitivity analysis is conducted where last status carried forward is used for imputation. Patients with missing age, date of randomization, sex or treatment assignment will be ignored. For additional endpoints those patients missing the endpoint will be ignored (for time to event analyses censoring will be used and aren't considered missing). For the subgroup analyses patients with missing subgroup variables will be lumped into a single group of "missing" in addition to the subgroup classifications.

For time-to-event analyses patients that have a competing event that dictates they cannot achieve a positive outcome (like death for time to hospital discharge), the patient will be assigned a no positive event outcome at the maximum time for the analysis. Patients not achieving an absorbing event that become lost-to-follow up will be censored at the last known time (unless otherwise specified for the analysis).

#### [12.10. Definition of times](#)

Adherence and per protocol analyses will rely on assessment of drug administration by the end of the first full study day after randomization. Post-randomization day 1 is referred to as study day 1 and constitutes the 24-hour period commencing at midnight of the day after randomization.

#### [12.11. Post-randomization analyses](#)

Participants who are randomized to receive one strategy may in fact be treated with another strategy based on health status and provider discretion. Co-interventions during the treatment period (e.g., aspirin, corticosteroids, IL6 antagonists, anticoagulants and their dosing) may modify the benefit or harm of P2Y12. Exploratory analyses will estimate the causal effect of the treatment for these patients using marginal structural modelling techniques. These techniques use inverse probability weighting methods that are based on patient-level covariates to create comparable groups for the analysis.

Anticoagulant treatment will be classified as based on the following dosing equivalents categorization: (1) standard prophylactic, (2) intermediate prophylactic, (3) subtherapeutic, and (4) therapeutic. The criteria for each categorization for each anticoagulant are given in Appendix B. Based on sample size, may collapse groups for analyses

## 12.12. Heterogeneity of treatment effect

The heterogeneity of the treatment effect will be evaluated in the following a priori defined subgroups:

- Age (< 50 years, 50-70 years, > 70 years)
- Sex
- Invasive mechanical ventilation at baseline for severe cohort
- For moderate (the amount of O2 required, no O2, > 0 but <= 2, >2)
- Heparin dosing during day 1. Categorized as therapeutic if defined as therapeutic at any time during day 0 or 1.

Additional exploratory subgroup analyses will include the following:

- Race/Ethnicity
- D-dimer levels
- Markers of inflammation (CRP, ferritin)
- Baseline troponin
- BMI
- Shock (use of vasopressors or inotropes at baseline)
- Baseline chronic kidney disease
- Steroid administration for COVID-19 at baseline
- IL-6 inhibitor administration for COVID-19 at baseline
- If additional treatments are determined through other research to be beneficial before unblinding subgroups will be defined by those treatments.
- Sites with at least 80% ticagrelor use as assigned P2Y12 inhibitor vs. sites with less than 80% ticagrelor use
- Geographic (Europe, US+Canada, Central and South America)

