4.1 Description of Study Design

This trial design is built as a process – with the possibility of multiple interventions being investigated. It is an open label randomized trial of patients hospitalized for COVID-19 who are assigned to different treatment regimens.

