6.2 Duration of Therapy

Once participants are randomized to a treatment strategy (arm), they will remain on treatment for the duration specified by the relevant appendix. However, if a participant randomized to one arm develops an indication for a different strategy (e.g., thrombotic event, worsening clinical status), the participant will be treated based on institutional guidelines with any measures required by local clinical judgment.

7 Study Procedures and Schedule

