^{****}Strongly recommended as part of routine care, all values collected should be recorded

^{*****}Optional, listed in case report form

[#]or 14 days, whichever is earlier

[#]Participants may be assessed for functional status and quality of life that reflects baseline status pre-COVID illness and functional status and quality of life at 90 days, when contacted to ascertain vital status. (Instruments detailed in the manual of operations).

⁺Assessments indicated in the table above will be ascertained at discharge, or at 28 days, whichever comes first. Participants must be followed for vital status until discharged from the hospital or another care facility (if transferred on organ support) up to 90 days. To maximize retention, participants will be contacted intermittently post-discharge and that contact will be recorded in the EDC

⁺⁺Participants may be contacted to ascertain vital status.

A7.7 Potential Risks & Benefits

A7.7.1 Known Potential Risks

Participants are monitored as per standard of care to minimize the risk of bleeding or developing clots. The standard of care plus P2Y12 inhibitor group will receive both anticoagulation and antiplatelet therapy and thus may be at higher risk of bleeding.

A7.7.2 Known Potential Benefits

Accruing data suggest that platelets are hyperactive in the setting of COVID-19. The platelet transcriptome isolated from hospitalized patients with COVID-19 is more pro-inflammatory than the platelet transcriptome from matched controls without COVID-19. Additionally, biomarkers of platelet activity are correlated with incident thrombosis and all-cause mortality. This arm seeks to test the hypothesis that there is a benefit of antiplatelet therapy in addition to standard of care for decreasing adverse events, including macro and micro-thrombosis. This potential benefit is hypothesized to offset an increase in bleeding risk. All participants will be closely monitored by the study team and any changes in antiplatelet therapy will be discussed with the treating physicians

and/or clinical team. There is a potential direct benefit of identifying thrombus or bleeding more rapidly based on close study monitoring. This trial will contribute to the body of generalizable knowledge about the antiplatelet strategy to minimize the risk of thrombus and adverse events in patients with COVID-19.

A7.8 Event Adjudication

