### 6. Analysis Populations

For the purpose of this SAP, several analysis populations are defined.

1. **study confirmed (Primary)**. The study's primary analysis population includes all enrolled patients with confirmed COVID-19 randomized to either intervention and analyzed according to the intention-to-treat principle (i.e. according to randomly assigned treatment status, irrespective of actual treatment receipt).

It is recognized that the primary analysis includes both patient cohorts, moderate and severe. This analysis population will remain primary even if one cohort has a trigger before the other cohort. This is because the primary analysis uses Bayesian borrowing in which the

outcomes from both cohorts are used to estimate the separate ORs for each cohort. The primary analysis will be conducted by the unblinded statistician and the results for the cohorts with statistical triggers will be reported to the DSMB.

If both cohorts achieve a superiority or futility threshold at the same time, a sensitivity analysis including a common odds ratio, adjusted for severity will be conducted, in addition to the primary analysis of each cohort.

The following analysis populations will be defined for each public disclosure corresponding to each cohort being unblinded.

2. **study confirmed unblinded.** The subset of patients in the study confirmed population that belong to the cohort(s) being reported (i.e. those specific cohort(s) that have been unblinded for reporting). This population consists entirely of patients with laboratory-confirmed COVID-19 randomized to P2Y12 or usual care and analyzed according to the intention-to-treat principle.
3. **study confirmed and suspected unblinded** (exploratory sensitivity analyses only). The study population including patients with suspected but unconfirmed COVID-19 who belong to the cohorts that are unblinded for reporting.
4. **study per protocol for P2Y12.** This consists of the patients in the study confirmed unblinded population who have been treated as per protocol. In this analysis that is defined as 1) patients randomized to P2Y12 and who received at least 1 dose by Day zero (day of randomization) or Day 1 (first full day after randomization, **and** 2) patients randomized to usual care who did not receive a P2Y12 dose on or by the end of first full study day after randomization (Day 1).

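### The a priori heparin subgroup is set by dosing up to the end of the first full day after open-label randomization, so it is open to bias; the pre-randomization dose should define it

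*SAP*

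**What the plan says.** SAP 12.12 separates a priori subgroups from additional exploratory ones. Heparin dose is in the a priori list: "Heparin dosing during day 1. Categorized as therapeutic if defined as therapeutic at any time during day 0 or 1". The line names day 1 first and then classifies on day 0 or day 1.

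Two other SAP sections fix the timing. In section 6, the per-protocol definition identifies day 0 as the day of randomization: "received at least 1 dose by Day zero (day of randomization) or Day 1". Section 12.10 defines day 1: "Post-randomization day 1 is referred to as study day 1 and constitutes the 24-hour period commencing at midnight of the day after randomization". The window therefore starts on the day of randomization, partly before assignment, and closes up to 48 hours after it.

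The SAP treats comparable variables differently. In the a priori list, invasive ventilation for the severe cohort is taken at baseline. In the exploratory list, the steroid subgroup is "Steroid administration for COVID-19 at baseline" and the IL-6 inhibitor subgroup is worded the same way. Section 12.11, on post-randomization analyses, says that co-interventions during treatment ("anticoagulants and their dosing) may modify the benefit or harm of P2Y12" closes the list) may act as modifiers, and it plans exploratory inverse-probability-weighted analyses. Section 12.12 attaches no weighting and no post-randomization label to the heparin subgroup.

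**The concern.** A subgroup comparison keeps the protection of randomization only if assignment cannot change who is in the subgroup. Here it can, for anyone not already therapeutic before assignment.

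The protocol supplies the conditions. Section 4.1 states: "It is an open label randomized trial of patients hospitalized for COVID-19". Appendix 1 leaves standard of care, including anticoagulation, to local determination. A7.7.1 says P2Y12 patients receive anticoagulation and antiplatelet therapy together and "thus may be at higher risk of bleeding". Section 6.2 says that when a patient develops another indication, such as worsening status, "the participant will be treated based on institutional guidelines with any measures required by local clinical judgment". A7.3.2 asks for the first P2Y12 dose as soon as possible, so study drug may be given before the heparin class is settled. A clinician who knows the arm can weigh both arm and prognosis when choosing heparin intensity.

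At stake is one pre-specified question: whether the P2Y12 effect differs by heparin background. If dosing after assignment depends on both arm and prognosis, an interaction could appear where none exists, or a real one could be hidden. The a priori label would lend such a result more credibility than it deserves.

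**Working it through.** The plan gives no sample size, expected effect or dosing rates for this subgroup, so there is no figure to reproduce. The check is the timing logic followed by two illustrations.

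**Logic.** Under the any-time rule, a patient who is therapeutic on day 0 before assignment stays in the therapeutic class whatever follows. Only the others can be moved. Bias also requires that movement depend on arm and on prognosis together.

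**Illustration 1: step-down in the P2Y12 arm.** All inputs are assumptions.

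- Latent severity z ~ N(0,1); log-odds of a bad outcome = −1.2 + 0.8z in both arms, so there is no P2Y12 or heparin effect.
- 60% are intended therapeutic, independent of z and arm. A share f of these is already therapeutic before assignment.
- In the P2Y12 arm only, a nominal 5 to 20 points of the arm are stepped down. This is a mean probability of 5/60 = 8% to 20/60 = 33% among intended-therapeutic patients, applied only to the share 1 − f.
- The step-down probability is proportional to expit(z) (sicker more often), expit(−z) (less sick more often), or constant.
- Benefit OR in a class = control odds of a bad outcome ÷ P2Y12 odds, each averaged over the z-distribution in that class. The result is the OR in the therapeutic class ÷ the OR in the other class; the truth is 1.00.

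| Share already therapeutic (f) | Sicker stepped down more, 5 / 20 points | Less sick stepped down more, 5 / 20 points | Unrelated to prognosis |
|---|---|---|---|
| 1 | 1.00 / 1.00 | 1.00 / 1.00 | 1.00 |
| 0.75 | 1.015 / 1.062 | 0.985 / 0.942 | 1.00 |
| 0.5 | 1.031 / 1.127 | 0.970 / 0.888 | 1.00 |
| 0 | 1.062 / 1.286 | 0.942 / 0.782 | 1.00 |

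The share that actually changes class is the nominal figure times (1 − f). At f = 0.5 it is 2.5 to 10 points of the arm.

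**Illustration 2: escalation instead of step-down.** Assumed: among patients not therapeutic before assignment, half are high risk (event risk 40%) and half low risk (15%). Low-risk patients are escalated to a therapeutic dose by the end of day 1 in 20% of cases in both arms; high-risk patients in 50% of controls and 30% of P2Y12 patients. Nobody is therapeutic beforehand and there is no true effect.

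- Therapeutic class, control: size 0.5×0.50 + 0.5×0.20 = 0.35; events 0.25×0.40 + 0.10×0.15 = 0.115; risk 0.329, odds 0.489.
- Therapeutic class, P2Y12: size 0.25; events 0.15×0.40 + 0.10×0.15 = 0.075; risk 0.300, odds 0.429. OR = 0.489/0.429 = 1.14.
- Other class, control: size 0.65; events 0.25×0.40 + 0.40×0.15 = 0.160; risk 0.246, odds 0.327.
- Other class, P2Y12: size 0.75; events 0.35×0.40 + 0.40×0.15 = 0.200; risk 0.267, odds 0.364. OR = 0.327/0.364 = 0.90.
- Ratio of ORs = 1.27.

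If half are already therapeutic (assumed risk 27.5%), the ratio falls to 1.16. With high-risk escalation of 50% against 40%, it is 1.12 (none already therapeutic) or 1.08 (half). If escalation differs by arm but not by prognosis, it is 1.00.

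**With classes set before randomization**, membership cannot depend on arm, and the OR in each class is 1.00 in both models.

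**The case against.** The case against has five parts.

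- **The route is not documented.** No passage says heparin changes with assignment, and SAP 4.2 gives both arms anticoagulation at the level recommended for the illness state. The bleeding statement comes from the Arm C appendix, which excludes moderate illness and regards prophylactic dosing as standard for severe patients, so there may be little therapeutic heparin to step down. Protocol 6.2 suggests added treatment for worsening rather than step-down. This stands as a limit on what can be claimed, but open-label, locally chosen dosing is enough to leave the comparison unprotected.
- **The 60% share fits neither cohort.** SAP section 6 pairs therapeutic dosing with moderate illness and prophylactic dosing with severe illness. With the same per-patient step-down (8% to 33%, f = 0.5, sicker more often), the ratio is about 1.01 to 1.07 if 10% are intended therapeutic and 1.10 to 1.26 if 90% are. This is a fair criticism of the illustration, and it cuts both ways.
- **The largest value is a corner case.** A ratio of 1.29 needs nobody therapeutic before assignment and a third of intended-therapeutic P2Y12 patients never reaching that dose by the end of day 1. This is correct.
- **Part is already covered.** SAP 12.11 plans weighted analyses, and SAP 10 compares anticoagulant dose by arm at baseline and during treatment. The day 0–1 window also matches the adherence convention. Neither makes the 12.12 comparison a randomized one.
- **The baseline rule changes the question somewhat and costs precision.** This stands, and the cost is given with the fix.

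**Conclusion.** The concern holds. As written, an a priori subgroup is partly defined by treatment chosen after a known assignment, and its within-group comparisons are not protected by randomization for patients not already therapeutic. The correct strength is open to bias, not shown to be biased: the documents give no dosing rates by arm, so size and direction are unknown.

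With half of the intended-therapeutic patients already on that dose, the step-down illustration gives a false ratio of odds ratios between 0.89 and 1.13. The bias vanishes if all are already therapeutic, or if dosing after assignment is unrelated to either arm or prognosis. These figures rest wholly on assumed shares and shifts.

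The scope is one secondary subgroup. The primary model in SAP 12.1 and the triggers in SAP 4.4 and 12.13 do not use this variable. The change is worth making because it is cheap and removes the problem at its source.

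**What to change.** 1. In SAP 12.12, define the a priori subgroup by the anticoagulant dose category (Appendix B) in force before randomization, and state the window once.
2. Show patients not yet on heparin as their own group. The four dose categories in SAP 12.11 contain no such class, so one has to be added.
3. Keep the day 0–1 version, labelled exploratory and post-randomization, beside the weighted analyses of SAP 12.11.
4. Tabulate by arm how many patients change category between randomization and the end of day 1. Similar movement in the two arms would largely ease the concern; a clear difference would be a warning.

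The cost is SAP wording and one table. SAP 10 already plans to summarize anticoagulant drug and dose at baseline, but gives baseline no clock time there; it must be tied to before randomization. The contents of Appendix B are not visible in the public copy, so its fit to a pre-randomization dose needs checking by the authors.

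The statistical price is precision. Enrollment is allowed within 72 hours of admission or of a positive test (Protocol 5.1), so an unknown number will not yet be on their intended dose and will leave the therapeutic-versus-not contrast. If a share s of each group is already on its dose, the standard error rises by 1/√s: 1/√0.75 = 1.15 at 75% and 1/√0.50 = 1.41 at 50%.

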## 12.13. Adaptive analyses

The goal for the P2Y12 arm is to determine if it is a safe and effective treatment for hospitalized patients with COVID-19.

### **Efficacy and Futility Monitoring Plan for P2Y12 Anti-Platelet treatment**

The efficacy goal of the P2Y12 arm is to determine if it improves the clinical outcome for hospitalized patients with COVID-19 as measured by the primary outcome, organ-support free-days (OSFDs). There is also the key secondary efficacy goal which is to understand if P2Y12 reduces major thrombotic events and negatively increases bleeding rates.

The hypothesis that P2Y12 reduces organ dysfunction through inhibition of microthrombi in capillaries led to the selection of the primary OSFD outcome. The thrombotic endpoint is testing the hypothesis that the risk of arterial and venous (small, medium and large vessel) thrombosis is reduced with P2Y12.

**Key Secondary Efficacy endpoint:** a composite major thrombotic event (TE) endpoint of death, pulmonary embolism, systemic arterial thromboembolism, myocardial infarction, or ischemic stroke collected during hospitalization or at 28 days after enrollment.

### **Stopping Rules for Efficacy**

The trial has been designed to separately test the efficacy of P2Y12 with respect to OSFD within two patient cohorts: patients with moderate or severe illness.

The P2Y12 arm will be declared superior to the usual care arm within a specific cohort if the posterior probability of superiority within the cohort is greater than 0.99.

There are no efficacy stopping boundaries for a cohort based on the key secondary endpoint of major thrombotic events or death. The key secondary endpoint is addressed only when futility has been declared for the organ-support free-day endpoint.

